7.1.6 Baseline Symptoms

Baseline symptoms are defined as those present at the closest time before the start of study drug administration.

7.1.7 Eastern Cooperative Oncology Group (ECOG) Performance Status

The investigator or qualified designee will assess ECOG status (see Appendix B) as specified in the Schedule of Events.

7.1.8 Concomitant Medications Review

The investigator or qualified designee will record medication, if any, taken by the subject starting at screening until end of trial treatment. All medications related to reportable SAEs should be recorded as defined in the SAE section of the protocol.

7.1.9 Adverse Event Review

The investigator or qualified designee will assess each subject to evaluate for potential new or worsening AEs as specified in the Schedule of Events and more frequently if clinically indicated. Adverse events will be collected from the time of consent until 30 days after last dose or until subsequent anti-leukemic therapy for those failing to show adequate response.

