5.4 PARTICIPANT WITHDRAWAL OR TERMINATION

5.4.1 REASONS FOR WITHDRAWAL OR TERMINATION

Subjects may withdraw consent at any time for any reason or be dropped from the trial at the discretion of the investigator should any untoward effect occur that may jeopardize participant safety. In addition, a subject may be withdrawn by the investigator if enrollment into the trial is inappropriate, the trial plan is violated, or for administrative and/or other safety reasons.

A subject must be discontinued from the trial for any of the following reasons:

- The subject or legal representative (such as a parent or legal guardian) withdraws consent
- Unacceptable adverse events
- Intercurrent illness that prevents further administration of treatment
- Investigator's decision to withdraw the subject
- The subject has a confirmed positive serum pregnancy test
- Noncompliance with trial treatment or procedure requirements
- The subject is lost to follow-up
- Administrative reasons

The End of Treatment and Follow-up visit procedures are listed in the Schedule of Events and Section 7.3 (Visit Requirements). After the end of treatment, each subject will be followed for 30 days for adverse event monitoring. Subjects who discontinue for reasons other than progressive disease will have post-treatment follow-up for disease status and toxicity up to 30 days. Follow-up rules will apply unless participant initiates a non-study cancer treatment, withdraws consent, or becomes lost to follow-up (unsuccessful attempts to contact for 3 months). After documented disease progression, each subject will be followed 12 months for overall survival until death, withdrawal of consent, or the end of the study, whichever occurs first.

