7.3.3 FOLLOW-UP

After the end of treatment assessment, all subjects will be followed with procedures and physical examinations per standard of care.

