7.3.7 SCHEDULE OF EVENTS TABLE

Procedures: Day:	Screening^a	1	2	3	4	5	6	7	10	28	29+ⁱ	End of Treatment/ Early Term.^g	Follow- Up
Informed consent	X												
Demographics and Medical History	X												
Baseline Symptoms ^b		X											
day Performance Status	X												
Concomitant Medication Review	X	Assess throughout Induction and Consolidation											
Review Adverse Events ^c		Assess throughout Induction and Consolidation										X	
CPX-351 Administration ^d		X		X		X							
Physical Examination	X												
Serum pregnancy test ^e	X												
Vital signs (temp, pulse, resp, BP, weight)	X	X		X		X						Per SOC	
Height	X												
12-lead EKG	X												
Echocardiography/MUGA	X										X ^l		
CBC with differential	X	X	X	X	X	X	X	X	X	X	X	Per SOC	
Serum chemistry testing ^f	X	X	X	X	X	X	X	X	X	X	X	Per SOC	
LDH, uric acid, magnesium, phosphorus	X	X	X	X	X	X	X	X				As needed	
Coagulation studies (PT/INR, aPTT, fibrinogen)	X												
Urinalysis with microscopy	X												
Bone marrow biopsy ^k	X										X		
CT or PET/CT Scan ^m	X										X		
Correlative studies ⁿ	X ^{1,2,3}										X ³		
CSF for ALL involvement/IT chemo ^j	X								X				
Follow-Up													X

- a. Screening assessments will be performed within 28 days of the dose of study drug Day 1. Any standard of care procedure performed within 28 days of Day 1, may be used for screening/eligibility even if performed prior to consent.
- b. Baseline symptoms are defined as those present at the closest time before the start of study drug administration.
- c. Adverse event data will be captured from the time of consent until 30 days after the last dose of CPX-351.

- d. CPX-351 induction therapy will only be administered to a subject following hospital admission. One induction will be administered. Patients with a CR, CRi, PR or determined by the PI to be experiencing clinical benefit after induction, may receive up to 3 consolidation treatments, all administered as an outpatient. First consolidation must be administered no earlier than 35-75 days after day 1 of induction. Second and third consolidations will be administered no earlier than 35-56 days after the start of the previous consolidation.
- e. Serum pregnancy test will be performed on females of childbearing potential (FCBP). A FCBP is considered when a sexually mature female: 1) has not undergone a hysterectomy or bilateral oophorectomy; or 2) has not been naturally postmenopausal for at least 12 consecutive months.

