8 ASSESSMENT OF SAFETY

8.1 SPECIFICATION OF SAFETY PARAMETERS

8.1.1 DEFINITION OF ADVERSE EVENTS (AE)

An adverse event means any untoward medical occurrence associated with the use of an intervention in humans, whether or not considered intervention-related (21 CFR 312.32 (a)).

The investigator or qualified designee will assess each subject to evaluate for potential new or worsening AEs as specified in the Schedule of Events and more frequently if clinically indicated. Adverse experiences will be graded and recorded throughout the study and during the follow-up

period. The descriptions and grading scales found in the revised NCI Common Terminology Criteria for Adverse Events (CTCAE) version 5.0 will be utilized for adverse event reporting. (<http://ctep.cancer.gov/reporting/ctc.html>)

Toxicities will be characterized in terms regarding seriousness, causality, toxicity grading, and action taken with regard to trial treatment.

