8.4 REPORTING PROCEDURES

8.4.1 ADVERSE EVENT REPORTING

Adverse event documentation will be performed by entry into the Moffitt OnCore electronic database. Reporting of adverse events to the FDA for IND renewal will occur annually by a report obtained from the AEs collected in OnCore. Reporting to Jazz Pharmaceuticals will be as noted in the section on AEs of special interest.

All AEs will be documented on a paper log with columns for the replication of the fields in the OnCore AE data form. The treating physician/investigator will review the log for accuracy and assign CTCAE grade and the attribution of a study agent to the AE.

Adverse events for the purpose of this study will be reported from the time period beginning when the consent form is signed until 30 days after study drug discontinuation.

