10.4.3 ANALYSIS OF THE SECONDARY ENDPOINT(S)

- Minimal Residual Disease (MRD) will be studied as a dichotomous endpoint using a cutoff of 1×10^{-4} cells/transcripts as the lower limit for residual leukemia, and presented as the percentage of patients reaching this landmark as their best response. MRD assessment will be obtained with each bone marrow biopsy assessment, as described below.
- Progression Free Survival and Overall Survival will be reported as per Cheson and Lugano Criteria, and analyzed using a standard Kaplan-Meier approach. Patients will undergo bone marrow biopsy evaluation after each cycle of therapy per standard of care to facilitated assessment. Patients achieving CR/CRi at the end of consolidation with marrow involvement will have follow-up bone marrow biopsy evaluation every 3 months in the first year following their last cycle of therapy, and every 6 months in the subsequent 2 years following their last cycle. Patients who remain in remission greater than 3 years from their last cycle of therapy will have bone marrow biopsy evaluation performed as needed. Patients without marrow involvement will have follow-up imaging (CT or PET/CT) every 3 months in the first year following their last cycle of therapy, and every 6 months in the subsequent 2 years following their last cycle. Patients progressing to allogeneic transplant following therapy will be censored at the time of conditioning.
- Safety will be continually assessed during the course of induction and consolidation cycles. Safety assessment will continue at a minimum of every 3 months for those who do not progress to allogeneic transplant or alternative therapy.

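### The special-interest events have two conflicting definitions and no single collection period, so the counts in the 10.4.4 table depend on which section is followed

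*Combined protocol and SAP*

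**What the plan says.** **Definitions.** Sections 2.2 (Rationale) and 8.4.4 (Events of special interest) each describe the same two events:

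| Event | Section 2.2 | Section 8.4.4 |
|---|---|---|
| Cardiac | Heart failure with symptoms, together with an ejection-fraction fall above 10%; carries a 42-day condition counted from start of therapy | Heart failure with symptoms and/or ejection fraction below 50% or a fall above 10%; no time condition |
| Aplasia | Hypocellular marrow with counts not recovered, more than 42 days after therapy starts | The same finding, more than 42 days after the start of induction or of a consolidation cycle |

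Section 10.4.4 puts special-interest events in a table but cites neither definition and gives no window. Section 8.4.1 points to the special-interest section for reports to the drug manufacturer.

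**Collection period.**
- 7.1.9: "Adverse events will be collected from the time of consent until 30 days after last dose or until subsequent anti-leukemic therapy". The sentence goes on to limit the second limb to patients without an adequate response.
- 7.3.7, footnote c: "Adverse event data will be captured from the time of consent until 30 days after the last dose of CPX-351".
- 8.4.1, and 8.3 in the same terms: from when "the consent form is signed until 30 days after study drug discontinuation".
- 5.4.1: "After the end of treatment, each subject will be followed for 30 days for adverse event monitoring". Patients who stop for reasons other than progression get "post-treatment follow-up for disease status and toxicity up to 30 days". These rules lapse once non-study cancer treatment begins.
- 8.1.1: "Adverse experiences will be graded and recorded throughout the study and during the follow-up" period. Section 7.3.3 then says: "After the end of treatment assessment, all subjects will be followed with procedures and physical examinations per standard of care".
- 10.4.3: "Safety assessment will continue at a minimum of every 3 months for those who do not progress to allogeneic transplant or alternative therapy".

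**The concern.** Safety is a listed secondary endpoint (4.2.2, 10.2), and 10.5 says the pilot is meant to give a preliminary view of safety in support of a larger study. The 10.4.4 table is where that view will be read. If the table's terms have two definitions and its window has several, two analysts who both follow the plan can report different counts from the same patients.

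There is a second problem of timing. The narrowest collection rule stops before one of the events can meet its own definition. A zero in the aplasia row could then mean that no patient had aplasia, or that general collection had stopped before the event could qualify.

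**Working it through.** The plan gives no figure to reproduce here. The check is day arithmetic plus a side-by-side reading.

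**Inputs.** Last dose on Day 5 of induction and Day 3 of consolidation (6.1.7). Collection to 30 days after last dose (7.1.9; 7.3.7 footnote c). Threshold of more than 42 days (2.2, 8.4.4). First consolidation no earlier than 28 days after induction starts (6.1.9, 7.3.2.11) or 35 days (7.3.7 footnote d); the documents give both, so both are shown. Treatment-phase marrow on Day 28, with up to 7 days' allowance in consolidation (footnote k). Start of therapy in 2.2 is read as the first study dose.

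**Step 1: when the last-dose window closes.** Elapsed days from cycle start = (last-dose day − 1) + 30.
- Induction: (5 − 1) + 30 = 34.
- Consolidation: (3 − 1) + 30 = 32.

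The threshold is first met at 43 elapsed days, or 42 if study Day 43 is meant. The shortfall is 42 − 34 = 8 to 43 − 34 = 9 days after induction, and 42 − 32 = 10 to 43 − 32 = 11 days after consolidation.

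**Step 2: whom this touches.**
- 8.4.4 clock, which restarts each cycle: aplasia cannot first qualify inside the last-dose window of a patient's last cycle.
- 2.2 clock, from start of therapy: any consolidation carries the window to at least 28 + 2 + 30 = 60 days (35 + 2 + 30 = 67 under footnote d), past 42. Only induction-only patients are affected.
- Cardiac event: no gap under 8.4.4, which sets no time. Under 2.2, the same gap in induction-only patients.

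Heart failure beginning on Day 45 (44 elapsed days) in an induction-only patient is outside footnote c. It is inside 10.4.3 unless transplant or other therapy has begun.

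**Step 3: the same patient under both definitions.**
- Ejection fraction falls by more than 10% with no symptoms: counted under 8.4.4, not under 2.2. This does not depend on how the 42-day phrase is read.
- Hypocellular marrow on Day 28 of the first consolidation, counts not recovered: at least 28 + 27 = 55 days from start of therapy, so it meets 2.2 as worded; but it is 27 to 35 days into its own cycle, so it does not meet 8.4.4.

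**Step 4: subsequent therapy.** Section 7.1.9 writes a stop into the collection rule, for inadequate responders only. Section 5.4.1 ends follow-up at non-study cancer treatment whatever the response. The end-of-treatment visit moves earlier if new therapy starts (7.3.2.17, footnote g). Section 10.4.3 excludes patients who go on to transplant or alternative therapy. Footnote c, 8.3 and 8.4.1 are silent.

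**Step 5: size.** If ten patients are dosed, one event counted or not moves the proportion by 1/10 = 10 percentage points. The denominator is all dosed patients (10.3) and can exceed ten, because replacement is allowed (5.4.2, 10.6.1).

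**The case against.** Several counter-arguments have weight.

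- *Most cut-offs are the same 30 days.* Last dose, drug discontinuation and end of treatment can be read as one event. A reader might infer from the differing words that every section sets a different cut-off; the documents do not show that. The follow-up period in 8.1.1 may be the 30-day toxicity follow-up in 5.4.1, and the end-of-treatment visit's 10-day allowance is a visit window that need not extend collection. The firm conflict is between the last-dose texts and 10.4.3.
- *New therapy shortens follow-up.* Sections 5.4.1, 7.3.2.17 and 10.4.3 all point that way, so a reader who inferred that the direction is unknown would be wrong. What remains is that the stop is worded for different patients in different places and is missing from three of the collection texts.
- *Aplasia would not be missed.* The cytopenia behind it can be expected to begin inside the 30 days; 8.3 follows open events to resolution; 8.4.4 sets no end date for reporting; and induction patients stay in hospital until marrow recovery. This stands against any claim that cases will be lost. It does not settle whether an event that first meets its definition after the cut-off goes into the table.
- *Section 2.2 is background, and 8.4.1 treats 8.4.4 as the special-interest section.* That may suggest 8.4.4 is the operative text. But 2.2 uses the same term with its own criteria, and nothing gives 8.4.4 precedence or links it to 10.4.4. The consolidation marrow example does take 2.2 literally, since 6.1.9 starts consolidation at blood-count recovery; the cardiac example needs no such reading.
- *All endpoints are exploratory, and no halting rule uses these counts.* True. That limits the consequence to the safety description.

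**Conclusion.** The point holds as an internal inconsistency that should be corrected. The two definitions differ for both events on their face, and the collection texts fall on both sides of the 42-day threshold, so the 10.4.4 counts are not determined by the plan. With on-schedule dosing the last-dose window falls 8 to 9 days short of the aplasia threshold after induction and 10 to 11 days short after consolidation. A delayed last dose (6.1.8) or a later anchor narrows or closes that gap.

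A reader might go further and infer that aplasia or heart failure cases will go unrecorded, or try to say how many of the ten patients are exposed. The documents support neither. Open-event follow-up and the open-ended reporting duty make loss uncertain, and the number of induction-only patients is not given. What can be said is that each event whose status turns on the choice of text is worth about 10 percentage points.

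**What to change.** 1. Reconcile 2.2 and 8.4.4 into one definition and one clock for each event, say how days are counted, and cite that definition in 10.4.4. Which definition is right is for the sponsor; this review takes no position.
2. Reconcile 5.4.1, 7.1.9, 7.3.7 footnote c, 8.3, 8.4.1 and 10.4.3 into one collection rule, with one defined anchor and one statement on the effect of subsequent therapy.
3. For the two special-interest events, make the collection period long enough for the chosen definition to be met, using standard-of-care records.
4. State in 10.4.4 that events qualifying after the general cut-off are tabulated, with those after new therapy shown separately.

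The cost is wording edits and a little more chart review, with no added procedures. Late events, above all those after new therapy, are harder to attribute to the study drug, which is why they are shown apart.

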7.1.10 Physical Exam

The investigator or qualified designee will perform a complete physical exam during the screening period. Clinically significant abnormal findings should be recorded as medical history.

7.1.11 Vital Signs

The investigator or qualified designee will take vital signs at screening and prior to the administration of each dose of trial treatment. Vital signs should include temperature, pulse, respiratory rate, weight and blood pressure. Height will be measured at screening only.

7.1.12 Laboratory Procedures

At screening laboratory procedures will include a CBC with differential, CMP (albumin, BUN, creatinine, alkaline phosphatase, ALT, AST, CO2, calcium, chloride, glucose, potassium, sodium, total bilirubin, total protein), LDH, uric acid, magnesium, phosphorus, coagulation studies, and urinalysis with microscopy. Laboratory testing on day one and during the hospitalization period, EOT, and follow-up will be at physician discretion per standard of care.

7.1.13 Bone Marrow Biopsy

A bone marrow biopsy will be performed at screening and at day 28. If determined the subject has extramedullary disease (as permitted in inclusion criterion #4), biopsy of the involved area will be the method by which correlative samples will be obtained, provided this can be safely obtained. If extramedullary disease is confirmed and the bone marrow biopsy is shown to be negative prior to trial participation, no bone marrow biopsy will be required at day 28. If subject discontinues treatment early or progression of disease is suspected, a bone marrow biopsy will be done at the discretion of the investigator. During follow-up, bone marrow biopsies will be performed per investigator discretion.

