6.1.9 DURATION OF THERAPY

All patients completing induction will be evaluable for efficacy. Consolidation may be started at the time of hematologic recovery (28-75 days after start of induction) for those achieving a complete remission or complete remission with incomplete hematologic recovery. Consolidation cycles may be repeated at the time of hematologic recovery for a maximum total of 3 consolidation cycles.

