7.3.5 EARLY TERMINATION VISIT

If a subject terminates study participation for any reason prior to completion of the protocol treatment plan, any subsequent procedures or evaluations will be per physician discretion as part of standard of care. Evaluation of AEs will continue as outlined in Section 7.1.9.

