8.4.4 EVENTS OF SPECIAL INTEREST

1. **Cardiotoxicity:** Current studies estimate the risk of cardiotoxicity to be low, perhaps related to the liposomal formulation. However, given that patients will have likely had prior anthracycline exposure (up to a maximum of 368 mg/m² daunorubicin or equivalent), we will obtain baseline echocardiogram or MUGA to ensure adequate ejection fraction. Followup echocardiogram or MUGA will be performed in all patients with symptomatic heart failure, defined as follows: worsening 1) dyspnea on exertion, 2) orthopnea, and/or 3) paroxysmal nocturnal dyspnea - with following concomitant findings of fluid overload on exam not well explained by prior therapy (such as hydration related to an episode of sepsis), including: 1) development of a third heart sound, 2) jugular venous distention with positive hepatojugular reflex, 3) pulmonary rales, and/or 4) lower extremity edema (ref 31). Follow-up echocardiogram or MUGA prior to each cycle of consolidation will be performed for all patients exceeding 550 mg/m² daunorubicin (or equivalent) . Patients with an ejection fraction of <50% or a decrease of >10% from baseline will discontinue consolidation therapy. The development of symptomatic heart failure and/or decrease in ejection fraction to <50%, or >10% from baseline will be reported to Jazz Pharmaceuticals.
2. **Bone marrow aplasia:** Liposomal delivery of chemotherapy may facilitate increased deposition within hematopoietic stem cells, culminating in delay or failure to recover hematopoietic cell reconstitution following therapy. In particular, a hypocellular marrow without adequate count recovery >42 days from start of induction or consolidation cycles will be reported to the sponsor.

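### A fully dosed patient taken off the trial between day 5 and day 28 can miss the primary response assessment and be replaced, because sections 5.4.1, 5.4.2, 7.1.13 and 7.3.5 do not fit section 3

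*Combined protocol and SAP*

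**What the plan says.** **Text that requires the assessment.** Section 3 has remission evaluated by a day-28 marrow in all patients with medullary disease who receive at least one full cycle, and by CT or PET/CT in extramedullary disease. Section 10.4.3 calls for a marrow after each cycle, and section 7.3.2.9 and note k of the schedule of events list it. Section 6.1.9 adds: "All patients completing induction will be evaluable for efficacy". Appendix A makes a marrow assessment a condition for confirming CR or CRi.

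**Text that releases it.** Section 5.4.1 states: "A subject must be discontinued from the trial for any of the following reasons". The list includes "Unacceptable adverse events" and "Intercurrent illness that prevents further administration of treatment", and has no category for stopping treatment while staying on study. For a patient whose participation ends before the treatment plan is finished, section 7.3.5 says that "any subsequent procedures or evaluations will be per physician discretion as part of standard of care"; only adverse event evaluation is stated to continue. Section 7.1.13 says: "If subject discontinues treatment early or progression of disease is suspected, a bone marrow biopsy will be done at the discretion of the investigator".

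**Text on what remains.** Section 5.4.1 also says: "Subjects who discontinue for reasons other than progressive disease will have post-treatment follow-up for disease status and toxicity up to 30 days". It names no marrow, scan or assessment day. Section 5.4.2 permits replacement of patients who drop out before the day-28 response assessment is done.

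**The concern.** Induction dosing is planned for days 1, 3 and 5 (section 6.1.7), and the primary endpoint is read at day 28 (section 4.2.1). That leaves 23 days in which a patient can have received every induction dose and still be taken off the trial for toxicity or illness. One set of sections calls this patient evaluable and requires the marrow. Another makes the assessment optional and lets the patient be replaced. No rule says how the patient counts if it is not done.

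In an open-label, single-arm trial, an optional marrow is plausibly done more often when a remission is expected and less often when the patient is very ill. Missing outcomes would then gather among patients with toxicity, and replacement would remove those patients from the denominator. The estimated CR/CRi rate and the decision to expand on 4 responders among 10 both depend on that denominator.

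**Working it through.** **1. The route through the text.**
- Last induction dose: day 5. Response assessment: day 28. Gap: 28 − 5 = 23 days.
- Toxicity or illness in this gap can lead to removal from the trial under section 5.4.1.
- The treatment plan includes consolidation, so a patient removed in the gap has not completed it and section 7.3.5 applies. Its wording covers all procedures, and so also the day-28 CT or PET/CT.
- The 30-day disease-status follow-up, counted from a day-5 last dose, runs to day 5 + 30 = 35. It spans day 28 but requires no marrow or imaging. Section 5.4.1 ends it earlier if the patient starts other cancer treatment, withdraws consent or is lost to follow-up.
- Without a marrow, Appendix A does not allow CR or CRi to be confirmed in medullary disease.
- Section 5.4.2 then allows replacement. Section 10.4.2 bases the expansion rule on the first 10 treated patients, whereas section 10.5 plans for 10 evaluable ones.

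**2. The plan's own figures.** Section 10.4.2 gives an illustrative Simon design with n1 = 10, r1 = 3, n = 19, r = 9, for rates of 35% and 65% (section 10.4.1). With exact binomial probabilities:
- PET = P(X ≤ 3 | 10, 0.35) = 0.5138 (stated 0.514)
- Average N = 10 + (1 − 0.5138) × 9 = 14.38 (stated 14.38)
- Type I error = 0.0844 (stated 0.084)
- Beta = 1 − 0.9048 = 0.0952 (stated 0.095)

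The table reproduces. The chance of at least 4 of 10 is 1 − 0.5138 = 0.486 at 35% and 0.974 at 65%.

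**3. Lost patients replaced.** The documents give no rate of lost day-28 assessments. The figure of less than 10% in section 10.5 covers only failure to complete induction. The loss fractions below are therefore assumptions.

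Let p be the true rate, L the fraction of treated patients lost, and f the response rate among those lost. The rate among assessed patients is q = (p − L·f)/(1 − L). If loss is unrelated to response (f = p), then q = p and nothing changes. The worst case for upward bias is f = 0, so q = p/(1 − L). With p = 0.35:

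| L | q | P(at least 4 of 10) | Illustrative two-stage type I error |
|---|---|---|---|
| 0 | 0.350 | 0.486 | 0.084 |
| 5% | 0.35/0.95 = 0.368 | 0.536 | 0.114 |
| 10% | 0.35/0.90 = 0.389 | 0.589 | 0.155 |
| 20% | 0.35/0.80 = 0.4375 | 0.707 | 0.281 |
| 30% | 0.35/0.70 = 0.500 | 0.828 | 0.489 |

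**4. Lost patients kept as non-responders, no replacement.** If m of 10 are lost independently of response, at least 4 responders must come from 10 − m patients:

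| m | P(go) at 65% | P(go) at 35% |
|---|---|---|
| 0 | 0.974 | 0.486 |
| 1 | 0.946 | 0.391 |
| 2 | 0.894 | 0.294 |
| 3 | 0.800 | 0.200 |

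This is the price of counting them as non-responders when assessments still go missing. It is the reason to keep the assessment due as well as fix how it is counted.

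**The case against.** The strongest reply is that the plan does require this outcome. Sections 3 and 10.4.3 call for the marrow, the schedule lists it, and disease-status follow-up under section 5.4.1 reaches past day 28. This stands to the extent that the defect is a conflict between sections, not a plan that omits its primary outcome. It does not remove the conflict, because section 7.3.5 makes the same assessment optional and the 30-day follow-up names no test.

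Section 7.1.13 also fits the case imperfectly. A patient with all three doses given has no induction dose left to stop, and the sentence may only be meant to allow an extra, early marrow. That is fair, and section 7.3.5 is the firmer basis.

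The endpoints are labelled exploratory, the Simon table is illustrative, and reaching 4 of 10 only leads the funder to consider expansion. This limits the stakes, but the estimate and that decision still use the affected denominator.

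Three stronger readings are tempting and are not supported:
- A reader might infer that leaving the trial ends safety and PFS data. Section 7.3.5 continues adverse event evaluation, section 8.3 keeps a 30-day reporting window, and section 5.4.1 keeps disease-status follow-up for up to 30 days. That is shorter than the PFS schedule in section 10.4.3, but it is not an immediate end.
- A reader might infer from section 2.3.2 that losses of this kind have already occurred. Seven patients were treated, and 2 CR plus 3 PR reported as 83% is 5/6, whereas 5/7 is 71%. No reason is given for the seventh patient, who may have been awaiting assessment.
- A reader might set section 5.4.1 against section 8.4.4, where patients with a fall in ejection fraction "will discontinue consolidation therapy". That rule concerns treatment after the day-28 endpoint and says nothing about assessing induction.

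**Conclusion.** The point holds as an inconsistency with a consequence for the primary endpoint. A fully dosed patient removed between day 5 and day 28 can go without a response assessment and be replaced, although section 3 and section 6.1.9 treat that patient as assessed and evaluable. The assessment becomes optional; it is not forbidden.

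The size cannot be determined from the documents. At a true rate of 35%, the chance of meeting the expansion threshold stays at 0.486 if loss is unrelated to response. In the worst case for upward bias it rises to 0.589 with 10% lost and 0.707 with 20% lost. Those figures assume that every lost patient is a non-responder and is replaced. The upward direction is a reasonable expectation in an open-label trial, not something the documents show. The change should be made, given its low cost, but the point does not invalidate the design.

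**What to change.** Reconcile sections 5.4.1, 5.4.2, 7.1.13 and 7.3.5 with section 3, leaving every treatment-stopping rule as it is:
- In section 5.4.1, separate stopping study treatment from leaving the study.
- In sections 7.1.13 and 7.3.5, state that the already scheduled day-28 response assessment (marrow, or CT or PET/CT for extramedullary disease) stays due for every dosed patient who is alive and has not withdrawn consent. Where it would be unsafe, record it as not done, with the reason.
- In sections 5.4.2 and 10.3, state that a fully dosed patient without a day-28 assessment stays in the efficacy denominator as a non-responder and is not replaced.

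The cost is protocol wording; no visit or test is added. The downsides are that a scheduled assessment remains due after treatment has stopped, and that the reported CR/CRi rate may be slightly lower. If 1 or 2 of 10 assessments are still missing for reasons unrelated to response, the chance of reaching 4 responders at a true rate of 65% falls from 0.974 to 0.946 or 0.894.
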